7.7 Research-only Assessment Visits

As in any large clinical trial of usual care, some participants in both arms will not be present for all scheduled treatment visits. In an attempt to 'de-link' complete cost, utilization, and longitudinal drinking data collection from a naturalistic observation of these same usual care patterns, we will conduct 3 Research-only Assessment visits at week 13, 25 and 48. These visits will not hinge on a participant's treatment retention status, will be heavily incentivized to encourage participation (\$100 for time and travel), and will be conducted preferably in-person but alternatively by telephone if a participant is otherwise unwilling or unable to appear in clinic. These visits will be carefully scheduled apart from MM treatment visits, which are otherwise not incentivized beyond the provision of no-cost care and medication, so as to minimize the influence of extra assessments, attention, and the monetary research participation incentive on a participant's willingness to continue with MM. Participants will be paid \$20 for the initial screening visit after completion of all research assessments and \$20 after completing the randomization visit.

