8.0 Assessments and Outcome Measures (Table 2)

Table 2. Visit Frequency (weeks)	0	1 ⁺	3	5 ⁺	7	9 ⁺	13 ⁺	17 ⁺	21 ⁺	25	26	48
XR-NTX vs. O-NTX + MM visits	x [#]	x [#]	x	x	x	x	x	x	x	x	x*	
Research-only assessment visits							x [#]			x [#]		x [#]

- *Safety documentation research visit
- # Compensation provided
- + Medication Dispensed

A comprehensive panel of measures is planned including standard measures of drug and alcohol use, medical status, and on-going treatment services utilization. The Timeline Follow Back (TLFB), Alcohol Use Disorders Identification Test (AUDIT), and Obsessive-Compulsive Drinking Scale (OCDS) are all validated measures used to identify alcohol and drug use along with regular urine toxicology and breathalyzer tests. The ASSIST will be used to assess for substance abuse or dependence and PHQ-9 for psychosocial diagnoses. The Seek, Test, Treat and Retain (STTR) assessment will collect various demographic information for each participant. The Economic Form 90, Cost Survey, and World Health Organization Quality of Life Survey (WHOQOL) will be used to assess treatment and criminal history as well as to ascertain economic data for cost-effectiveness outcome measures. The Morisky Medication Adherence Scale (MMAS-8) will be administered to the O-NTX arm only, providing information on adherence to self-administered medications. Fagerström's test for nicotine dependence and recall of cigarettes per day will be used to assess smoking cessation measures. Adaptations of the Stages of Change Questionnaire (SOC) and Responses to Stress Questionnaire (RTS) will look towards patient motivation, self-efficacy, and coping skills. The DSM-V criteria for PTSD, Generalized Anxiety Disorder 7-Item Scale (GAD-7), and Perceived Stress Scale (PSS) will be used to assess PTSD. Throughout the treatment phase, all adverse events (AEs) will be recorded on an AE form at all treatment visits.

Screening Visit (week 0): Informed Consent Form, Consent Quiz, medication preference question, DSM-V diagnostic interview and checklist, demographics, ASSIST, PHQ-9, WHOQOL, Alcohol Use Disorders Identification Test (AUDIT), Obsessive-Compulsive Drinking Scale, Fagerström, SOC, RTS, Questionnaire, DSM-V checklist for PTSD, GAD-7, PSS, history and physical exam, vital signs, liver function (AST, ALT, GGT), urine toxicology, pregnancy test, blood alcohol breathalyzer.

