Randomization Visit (week 1): Medical Management initial visit progress note, baseline biomarkers (CDT, Asp40 OPRM1 genotyping), urine toxicology, and Economic Form 90.

Treatment Visits (week 3-25): Timeline Followback (TLFB), recall of cigarettes per day, Morisky Medication Adherence Scale (MMAS-8, O-NTX arm only), Medical Management follow-up visit progress note, Adverse Event form, labs (weeks 13 and 25 only, AST, ALT, GGT, CDT).

Research-only Assessments* (week 13, 25, 48): TLFB, Economic Form 90, AUDIT, OCDS, WHOQOL, Fagerström**, SOC**, RTS**, DSM-V checklist for PTSD**, GAD-7**, and PSS**.

**Only at weeks 13 and 25.

Banked Genetic and Biomarker Testing: At randomization, participants will provide two separate blood draws (3 teaspoons blood for each) for genotyping and biomarker testing. Each of these blood samples will be labeled with the subject ID number and the date of blood draw only. No identifiable or private health information will be included on the labs prior to and when sent out for testing. Blood samples for a single biomarker (CDT) for heavy alcohol use will be drawn at randomization, weeks 13, and 25, and kept frozen at secure NYUMC facility freezer. At the conclusion of enrollment for study, samples will be sent in large batches to the Medical University of South Carolina (MUSC) and [name], a consultant on this protocol, laboratory. Results filed under the study ID only will be communicated and entered into the study database. Whole blood samples for a single nucleotide polymorphism (SNP) at the mu opioid receptor, the A118G OPRM1 SNP, will likewise be frozen, banked, and shipped in batch fashion for analysis at MUSC by

[name]. All samples will be destroyed following analysis and not preserved for future use. Results from either CDT or OPRM1 will be for research purposes only, will not be considered in real-time or used for participant counseling, and will be analyzed at conclusion of the study as secondary biomarkers and genetic baseline predictors of treatment outcomes.

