8.2 Secondary Drinking, Adverse Events, and Measures: drinking measures will be evaluated at each monthly visit (TLFB), along with self-reported O-NTX adherence (MMAS-8) and adverse events. Liver function tests (aspartate transaminase (AST), alanine transaminase (ALT), gamma-glutamyl transferase (GGT) and carbohydrate-deficient transferrin (CDT) will be measured every three months (week 0/1, 13, and 25), with AST, ALT, and GGT results available in real-time to study physicians. CDT, a validated biomarker for heavy drinking,^{82,83,84} is not in use or available at either facility, and will not be reported to participants or study physicians, but rather used as a secondary marker of baseline and in-treatment heavy drinking. CDT represents a 'cutting edge' alcohol biomarker, and one not previously studied in the context of an XR-NTX treatment trial. Analysis and interpretation of CDT results will be coordinated with [name] and his laboratory. Likewise, baseline assessments of drinking severity and psychiatric function (OCDS,⁸⁵ MINI-SCID,⁸⁶ Form 90⁸⁷) and naltrexone mu receptor susceptibility (Asp40 OPRM1 genotyping) will be captured for research purposes only, and not integrated into the clinician's MM strategies.

8.3 Cost Effectiveness Outcomes: Economic data will be derived primarily from the Economic Form 90,⁸⁸ Non-Study Medical Service and HHC electronic medical records assessments, EQ-5D (functional status),⁸⁹ and a cost survey or standardized question querying patient reports of specific non-medical related costs (including lost/gained work, lost/gained dependent care, transportation costs, arrests, motor vehicle accidents) collected at baseline and at week 13, 25, and 48 assessments. The week 48 assessment is included to gain longitudinal, post-treatment cost, drinking, and functional data at a small cost to the overall study budget. Whenever possible, verification of productivity (paystubs) and medical costs (medical records) will be sought to corroborate self-report.

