9.0 Power and Sample Size

As in the original proposal and based on our recent feasibility study of XR-NTX in primary care² and the O-NTX treatment retention and adherence literature,^{6,7,19} including the single review by Roozen comparing the two medications,²⁸ we are powering this study on the assumption that XR-NTX is approximately twice as effective as O-NTX at achieving drinking reductions, including a good clinical outcome of abstinence or moderate-drinking-only during weeks 5-24, and also increased days abstinent and reduced rates of heavy drinking, drinks per drinking day, and drinks per day overall. This is

hypothesized to be mediated by superior naltrexone adherence. We predict based on our pilot data and the literature that 40-50% of patients will complete 24 weeks of treatment on XR-NTX, compared to <20% on O-NTX, based on O-NTX clinical trial and commercial refill data. We then estimate rates of the primary good clinical outcome of approximately 20% in O-NTX participants and 40% in the XR-NTX arm, roughly the same as adherence rates. This is based on our pilot data, in which 36 of 40 persons completing 12 weeks of XR-NTX qualified for the moderate-drinking-only good clinical outcome, and COMBINE, in which adherent oral naltrexone/MM patients reported high rates of the same moderate-drinking-only good clinical outcome during the final 8 of 16 weeks of the study. With 100 subjects per group, we anticipate power of 0.84 to detect a 20% absolute difference in the primary outcome based on the Fisher's exact test. These projected rates, however, are not well established, nor based on large datasets of heterogeneous alcohol populations, and therefore we have increased the target screening n to 468, with a very conservative assumption of 2 subjects screened for every 1 enrolled, for a target sample of N=234 and n=117 per arm, which increases the projected power to 0.90.

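### After baseline, the visit lists place the CDT sample only at treatment visits, so if followed as listed CDT is likely to be missing mostly in participants who have left Medical Management, and more often on O-NTX

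*Combined protocol and SAP*

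**What the plan says.** - **Treatment visits.** The visit-by-visit lists in Section 8.0 put "labs (weeks 13 and 25 only, AST, ALT, GGT, CDT") under Treatment Visits (weeks 3-25).
- **Research-only visits.** The list for these visits opens "Research-only Assessments* (week 13, 25, 48): TLFB, Economic Form 90, AUDIT, OCDS, WHOQOL" and goes on to further questionnaires. It names no blood test.
- **General timing statements.** Two other sentences give the weeks without a visit type. The paragraph on banked testing in 8.0 says "Blood samples for a single biomarker (CDT) for heavy alcohol use will be drawn at randomization, weeks 13, and 25". Section 8.2 says the liver tests and CDT "will be measured every three months (week 0/1, 13, and 25").
- **Purpose of the Research-only visits.** Section 7.7 separates them from MM visits and makes them independent of retention. They "will be heavily incentivized to encourage participation" ($100), with telephone as the fallback to attending in person.
- **Role of CDT.** Section 8.2 has it "used as a secondary marker of baseline and in-treatment heavy drinking". The study summary before Section 2.0 lists biomarkers among the between-arm secondary outcomes, and 10.1 promises CDT in the primary publication.
- **Expected retention.** Section 9.0 predicts that "40-50% of patients will complete 24 weeks of treatment on XR-NTX, compared to <20% on O-NTX".

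**The concern.** The trial is open-label and its primary outcome is self-reported drinking. CDT is the one laboratory marker that the protocol singles out as specific for heavy drinking, and neither participants nor study physicians see the result. Its value lies in being comparable between arms and in covering people who stopped coming.

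For the drinking calendar, the plan provides a backup: it is taken at both MM and Research-only visits, and 8.1 uses a research-only calendar for anyone who misses the week 25 MM visit. CDT has no such backup in the visit lists. It also has no missing-data rule: the rule in 10.1 that counts drop-outs as failures concerns the primary outcome, and CDT is not among the variables listed for the mixed model.

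A CDT comparison confined to MM attenders is selected on something that happens after randomisation and that the plan itself expects to differ at least two-fold between arms. It would say little about all randomised participants and could not check self-report among those who left.

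**Working it through.** **The plan's own figure.** The documents give no power or expected completeness for CDT. The only power figures concern the primary outcome: 0.84 at 100 per arm and 0.90 at 117 per arm, for 20% against 40% by Fisher's exact test. Exact enumeration at two-sided 5% (alpha is not stated, so this is assumed) gives 0.844 and 0.901. Both reproduce, and CDT timing does not affect them.

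**Inputs.** 117 per arm and completion of 40-50% (XR-NTX) and below 20% (O-NTX), all from Section 9.0. Completing treatment is used as a proxy for attending the week 25 MM visit. In-person attendance at Research-only visits is not given; 70-90% in both arms is an assumption.

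**Step 1: week 25 samples if drawn only at MM visits.**
- XR-NTX: 117 × 0.40 = 46.8 and 117 × 0.50 = 58.5, so about 47 to 58, with 50-60% missing.
- O-NTX: 117 × 0.20 = 23.4, so at most 23, with at least 80% missing.
- Together: at most 70 to 82 of 234 (30-35%), with missingness at least 20 to 30 points higher on O-NTX.

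**Step 2: precision.** Detectable difference in SD units at 80% power and two-sided 5% = (1.96 + 0.84) × √(1/n₁ + 1/n₂).

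| Samples (XR-NTX / O-NTX) | Detectable difference |
|---|---|
| 46.8 / 23.4 | 0.71 SD |
| 58.5 / 23.4 | 0.69 SD |
| 81.9 / 81.9 (70% in person) | 0.44 SD |
| 93.6 / 93.6 (80%) | 0.41 SD |
| 105.3 / 105.3 (90%) | 0.39 SD |
| 117 / 117 (all) | 0.37 SD |

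The first two rows are best cases for O-NTX, because the forecast there is an upper bound.

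**Step 3: selection, as an illustration.** Suppose CDT is elevated in 10% of completers and in a share e of drop-outs, the same in both arms (assumed). The attenders then show no difference. The difference among all randomised participants is (XR-NTX completion − O-NTX completion) × (e − 0.10):
- smallest case, 40% against 20% and e = 0.30: 0.20 × 0.20 = 4 points in favour of XR-NTX;
- largest case, 50% against 20% and e = 0.70: 0.30 × 0.60 = 18 points.

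Section 9.0 expects any benefit to work through adherence, and this is the kind of effect that an attenders-only comparison could miss.

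**Week 13.** The documents forecast no week 13 attendance by arm. The single-arm pilot had 56% receiving the month 3 injection (0.56 × 117 = 65.5), but there is no O-NTX counterpart, so no week 13 comparison is computed.

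**The case against.** The strongest reply is that the plan does not exclude drop-outs from CDT sampling. The general statements in 8.0 and 8.2 fix the weeks and leave the visit open, and the Research-only heading carries an asterisk whose note does not appear in the extracted text. This stands: a reader might infer that CDT is confined to MM attenders, and the documents do not say so. But the only visit-level instruction places the sample at treatment visits, and nothing provides for a draw after someone leaves MM.

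Second, completing medication is not the same as attending MM. Section 7.8 encourages participants to stay in follow-up for the full 24 weeks despite side effects or drinking, and 8.1 notes that the week 25 visit involves no prescribing. Attendance could therefore exceed the forecast in both arms. This also stands, and the counts are a projection.

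Third, a reader might call CDT the trial's only objective drinking measure. That goes too far. Section 8.0 describes validated scales used "along with regular urine toxicology and breathalyzer tests", although the visit lists name a breathalyzer only at screening, and GGT, AST and ALT are also laboratory measures.

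Fourth, assuming equal in-person attendance in both arms assumes away the imbalance. That is fair; it is why a range is shown and called an assumption. Telephone assessments will still yield no blood.

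Finally, the liver tests also serve safety monitoring and go to study physicians in real time. The selection argument concerns CDT, so the point does not extend to them.

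**Conclusion.** The concern holds for post-baseline CDT; the baseline sample is taken at randomisation. The visit lists and the general timing statements leave open whether participants who have left MM are sampled. Followed as listed, the CDT comparison would be selected on retention. On the protocol's forecast used as a proxy, that means roughly 47 to 58 against at most 23 samples at week 25 and a detectable difference of about 0.7 SD, against 0.44 to 0.39 SD if 70-90% per arm gave a sample in person. True MM attendance may be higher, which would narrow the gap.

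A reader might infer that the trial's main result is weakened. The documents do not support this: CDT is a secondary outcome, and the primary outcome rests on the drinking calendar with its own backup and drop-out rule. This is a cheap improvement to a promised secondary outcome.

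**What to change.** - **Sampling.** In Section 8.0, state that the already scheduled week 13 and week 25 CDT sample is drawn at the MM visit or the in-person Research-only visit, whichever is attended. Make the Research-only list, the banked-testing paragraph and 8.2 agree.
- **Analysis.** In 10.1, state that CDT is analysed in all randomised participants with a sample, whatever their retention, and that missing CDT is reported by arm.
- **Labelling.** In the same edit, reconcile 8.1, which speaks of a research-only assessment at week 26, with Table 2, which puts that assessment at week 25 and a safety documentation visit at week 26.

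**Cost.** Protocol wording and visit logistics. No participant gives more CDT samples than the schedule already names, but compared with the visit list as it stands there will be some added draws among those who have left MM. Telephone assessments still give no sample, so the gap narrows without closing, and the by-arm missing counts remain necessary.

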9.0 Power and Sample Size

As in the original proposal and based on our recent feasibility study of XR-NTX in primary care² and the O-NTX treatment retention and adherence literature,^{6,7,19} including the single review by Roozen comparing the two medications,²⁸ we are powering this study on the assumption that XR-NTX is approximately twice as effective as O-NTX at achieving drinking reductions, including a good clinical outcome of abstinence or moderate-drinking-only during weeks 5-24, and also increased days abstinent and reduced rates of heavy drinking, drinks per drinking day, and drinks per day overall. This is

hypothesized to be mediated by superior naltrexone adherence. We predict based on our pilot data and the literature that 40-50% of patients will complete 24 weeks of treatment on XR-NTX, compared to <20% on O-NTX, based on O-NTX clinical trial and commercial refill data. We then estimate rates of the primary good clinical outcome of approximately 20% in O-NTX participants and 40% in the XR-NTX arm, roughly the same as adherence rates. This is based on our pilot data, in which 36 of 40 persons completing 12 weeks of XR-NTX qualified for the moderate-drinking-only good clinical outcome, and COMBINE, in which adherent oral naltrexone/MM patients reported high rates of the same moderate-drinking-only good clinical outcome during the final 8 of 16 weeks of the study. With 100 subjects per group, we anticipate power of 0.84 to detect a 20% absolute difference in the primary outcome based on the Fisher's exact test. These projected rates, however, are not well established, nor based on large datasets of heterogeneous alcohol populations, and therefore we have increased the target screening n to 468, with a very conservative assumption of 2 subjects screened for every 1 enrolled, for a target sample of N=234 and n=117 per arm, which increases the projected power to 0.90.

10.0 Statistical and Cost Effectiveness Analysis

Preliminary analyses of balance: balance across the study on potentially prognostic baseline variables will be appraised using analyses of variance for continuous variables and log-linear models for discrete and ordinal responses. Variables for which significant differences were observed will be included as covariates in later analyses. Sometimes variables with strong clinical associations with the primary outcome are identified post hoc, and usually included in the analysis to reduce bias and improve efficiency (yielding smaller p-values and narrower CIs). Further, in mixed models there is always a possibility that an analysis will not converge. This danger is minimized by including in the model only essential covariates. Hence, before analyzing the primary outcome measure, the plan is to determine which predictive variables rise to a sufficient level of importance.

10.1 Hypothesis 1: The rate of the primary good clinical outcome will be approximately twice as high among participants receiving XR-NTX compared with those receiving O-NTX. (Primary Aim, Treatment Effectiveness: To evaluate the effectiveness of XR-NTX vs. O-NTX in producing a primary good clinical outcome defined as abstinence or moderate drinking (≤ 2 drinks/day, men; ≤ 1 drink/day, women; and ≤ 2 heavy drinking occasions/month), during the final 20 of 24 weeks of primary care-based Medical Management for alcohol dependence)

The primary outcome measure of this study is a binary measure of success defined by abstinence or moderate drinking only, as measured by the TLFb, with drop-outs from MM and research-only assessments assumed to have resumed baseline rates of heavy drinking, and therefore defined as good clinical outcome failures. Our analytic approach will be an intention-to-treat comparison of all randomized participants (N=234). The analysis will utilize a logistic regression with an indicator variable for treatment and covariate terms for baseline potential prognostic indicators that are not stratified for at randomization, including AA ethnicity, lead-in abstinence, medication preferences, baseline drinking severity, in-trial specialty treatment involvement, clinical site, and OPRM1 genotype. If the coefficient of treatment is significant the null hypothesis of equal treatment effect is rejected. Odds ratios will be calculated to quantify the risk to treatment failure of significant predictors (Secondary Aim 2: Patient-Level Predictors of Effectiveness: To identify patient-level characteristics associated with effectiveness in both arms). To differentiate time to a good clinical outcome failure, we will use a "cure model." The form of a cure model is $H(t) = 1 - p + pS(t)$; where $H(t)$ is the probability of failure at a time greater than t , p represents the probability of failure, and $S(t)$ the distribution of time to failure, conditional on failure occurring. The parameters will be estimated based both on Kaplan Meier methods and parametrically. The equality of the values of p for the two treatment arms will be tested using a nonparametric likelihood ratio test. For the parametric test, a logistic will be used to model p and a Weibull survival distribution will be used to model time to failure, $S(t)$. Both allow the use of covariates, which will complement the above logistic regression approach.

As originally proposed, naltrexone appears most effective at reducing heavy drinking, as opposed to producing complete abstinence, and all traditional alcohol treatment trial clinical endpoints, including continuous drinking and heavy drinking variables, as well as the CDT biomarker, which is specific for heavy drinking, are of great interest, and will be reported in the primary publication from this trial. In addition, rates

of medication treatment adherence, and an alternative good clinical outcome, treatment retention AND no heavy drinking, will be reported. Treatment differences in % days abstinent, overall % heavy drinking days, time to first drink, and time to first heavy drinking day, will be compared using mixed model repeated measures (MMRM) analysis including terms for subject, treatment, and time by treatment interaction, and covariate terms for baseline variables. To examine differential treatment effects at each week, we will perform tests of simple main effects. The MMRM will assume a means model, an unstructured covariance matrix and estimation will be based on restricted maximum likelihood. The baseline values will be adjusted by the overall mean. The assumptions relating to the mixed-effects model will be reviewed by examining residual scatter plots to examine deviations from normality and to assess lack-of-fit. In case of violation of assumptions, a randomization test will be performed based on the same MMRM.

10.2 Hypothesis 2: XR-NTX treatment will be more cost effective than O-NTX. (Secondary Aim 1: Cost Effectiveness. To estimate the incremental cost effectiveness of XR-NTX vs. O-NTX both in conjunction with primary care-based medical management of alcohol dependence).

We will estimate the incremental cost-effectiveness of XR-NTX compared to O-NTX. In technical terms the incremental cost-effectiveness is the ratio of incremental costs to incremental benefits; in lay terms, the incremental cost-effectiveness indicates the 'bang for the buck' of XR-NTX compared to O-NTX. The incremental cost-effectiveness of XR-NTX treatment compared to O-NTX treatment is equal to (Cost of XR-NTX minus Cost of O-NTX) divided by (Effectiveness of XR-NTX minus Effectiveness of O-NTX).

Cost-effectiveness analysis requires estimates of costs and estimates of effectiveness. Consequently, we will use primary data analyses from this study (Specific Aim 1 in the proposal) to inform costs and effectiveness estimates in the short-term, and we will synthesize these short-term estimates with published reports that allow us to estimate the longer-term, downstream costs and effects of the changes in alcohol consumption observed in Specific Aim 1. We will alternatively use societal and payer perspectives for assessing costs, and we will use the standard discount rate of 3% for costs and benefits.⁹⁰ The discount rate reflects the time preference with regard to costs and benefits (i.e., a dollar today is worth more to most people than an inflation-adjusted dollar at some time in the future). All costs will be inflated to 2011 US \$ using alternatively the consumer price index (CPI) for all goods and services and the CPI for Medical services (reflecting the ongoing debate over whether the Medical services CPI overestimates inflation because of the difficulty of discriminating the effect of service improvement from service inflation).

Short-term estimates of costs and effectiveness of XR-NTX compared with O-NTX. Short-term estimates of costs and effectiveness will be obtained from primary analysis of data from the trial proposed in Aim 1, using a combination of pre-specified medical record and survey endpoints. Cost assessment will be conceptually similar to recently published analyses of the COMBINE interventions,^{36,37,38} and will include medical and non-medical costs as well as payer and societal costs. Effectiveness assessment will include alcohol consumption measures as described elsewhere in this proposal, as well as quality of life. Quality of life will be assessed using the EQ-5D. The EQ-5D is among the most commonly used quality-of-life measure for informing cost-effectiveness analyses because it has minimal respondent burden, is well validated, and it yields utilities (preference-based measures on a scale of 0 to 1), the desired input for cost-effectiveness models. Because costs are skewed, incremental costs will be assessed using ordinary least squares (OLS) and median regression models with covariates for treatment intervention and other relevant factors, and conditional models may be used because of cost data that may include "zeros."

Longer-term estimates of costs and effectiveness. To estimate the comparative effectiveness of XR-NTX relative to O-NTX over longer time horizons than are reflected by our data, we will incorporate these short-term results within a state-transition (Markov) computer simulation of outcomes that enables a cohort of hypothetical alcohol-dependent patients to be followed over time until death, and to be exposed to alternative alcohol interventions for specified time durations beyond the week 24 assessment. We will develop this simulation expressly for this proposal, drawing on our experience creating, validating, and using other computer simulations assessing the impact of alcohol interventions on long-term costs and benefits.^{91,92,93,94,95} The simulation will be able to aggregate the lifetime benefit of remitting alcohol dependence for designated periods of time using trial endpoints (e.g. frequency of heavy drinking days), and also can quantify benefits of the levels of improvement short of full remission (e.g. if alcohol

dependence remits but the patient still is an at-risk drinker). The simulation will estimate lifetime costs and benefits over a lifetime horizon, measured in both life-years and quality-adjusted life-years. (Quality-adjusted life years is a preference-based, quality of life metric that considers quality of life simultaneously with quantity of life, and instantiates the notion that a typical person would trade away some quantity of life to get a greater quality of life.) In sensitivity analyses we will consider time horizons shorter than lifetime (10 year and 20 year) because these horizons are sometimes preferred by decision makers, even though the longer, lifetime horizon is advocated by the Panel on Cost-Effectiveness in Health and Medicine.⁷⁷

Further considerations of the cost-effectiveness approach: The above simulation will assume that the costs and benefits observed in the trial have varying levels of persistence. In the most pessimistic scenario, any treatment effect observed in the trial would wane rapidly after the trial follow-up period, and therefore any benefits that accrue in the long-term would be attributable to the short-term effect, or, in the more optimistic scenario, any treatment effect observed would persist indefinitely, as long as the treatment is continued. Therefore, the simulation would aggregate incremental benefits of magnitude observed in the trial that are assumed to persist as long as the treatment is continued. The most optimistic, albeit unrealistic, scenario is that the treatment effect will persist indefinitely after the trial concludes, and no additional treatment would be necessary. Because this scenario is unrealistic, we will only perform analyses along these lines as sensitivity analyses; however, we will analyze scenarios in which persistence of treatment effect requires select treatment “boosters” of variable duration and frequency.

To aggregate the impact of remission of partial and/or complete alcohol dependence, the simulation will require estimates of the impact of alcohol dependence and other alcohol use disorders (e.g. at-risk consumption and harmful consumption) on quantity and quality of life, and on costs. These estimates will be based on published reports that have aggregated the impact of alcohol on the morbidity and mortality and costs of specific diseases with substantial risk attributable to alcohol (e.g., hypertensive heart disease, cirrhosis of liver, oral cancers, etc).⁹⁶ In addition, simulation input will also draw on published reports that have aggregated the impact of alcohol on morbidity, mortality, and costs of non-medical sequelae of alcohol consumption (e.g., motor vehicle collision, arrests)⁹⁷ As in our previously published simulation work, we develop the computer simulation for this proposal by incorporating the standard, stepwise procedure of *specification* (defining the structure and mathematical relationships of the variables in the model), *verification* (otherwise known as “debugging”; making sure the model performs consistently with expectations across a wide range of inputs, including “stress tests” when inputs may be deliberately set to extreme, clinically unrealistic values in an attempt to unmask flaws in the model), *parameterization* (inputting variable estimates based on relevant data or expert opinion), *calibration* (making sure model output is similar to observed clinical output in relevant circumstances), and *validation* (testing model performance in circumstances or clinical populations distinct from those used for model development).

Uncertainty: we will estimate 95% confidence intervals around point estimates of incremental cost-effectiveness using standard approaches in which vectors on the cost-effectiveness plane are identified corresponding to the 2.5th and 97.5th percentiles of incremental cost-effectiveness. We will also create corresponding acceptability curves, which denote the probability that a particular program or programmatic decision is favorable given a particular willingness to pay for health benefits.

If the trial is negative, what’s the purpose of Aim 2? It might be observed that, if an intervention is not effective, it is meaningless to estimate its cost-effectiveness. Therefore, it might appear that the scientific validity of Aims 1 and 2 are inter-dependent. However, in the event that Aim 1 produces negative results, we will employ the computer simulation developed for Aim 2 for a slightly different purpose. Rather than using the simulation to estimate the cost-effectiveness of XR-NTX versus O-NTX, we will instead use the simulation to ask “what is the minimum level of incremental effectiveness required for an intervention to deliver sufficient value?” so that Aim 2 remains scientifically relevant and useful for decision makers. For example, even if XR-NTX does not deliver significant improvements in effectiveness compared to O-NTX, we would use the simulation to infer what levels of incremental effectiveness would be necessary to deliver sufficient value, given particular assumptions about incremental costs. For example, if a new intervention cost \$100/month more than O-NTX, how many fewer heavy-drinking days would it need to reduce compared to O-NTX in order to deliver sufficient value (incremental cost-effectiveness ratio < \$100,000/QALY)? That way, simulation results can inform future trial design. This approach is detailed in our recent publication,⁹⁸ and is concordant with principles of value-of-information analysis.⁹⁹

10.3 Secondary Aim 2: Patient-Level Predictors of Effectiveness. The multivariate models described for Aim 1, while testing the main and subsidiary hypotheses, will also be used to identify patient characteristics associated with treatment success. We hypothesize a priori that there will be less robust effectiveness in both arms among women and African Americans, while pre-treatment abstinence, voluntary specialty alcohol treatment and Alcoholics Anonymous involvement (patients are not directly referred to ancillary treatment), and presence of the Asp40 OPRM1 SNP will be associated with treatment effectiveness. We also hypothesize that these positive associations will be more pronounced within the XR-NTX arm due to the sustained medication adherence following each injection. We note, however, that these analyses will be exploratory, as the study is not powered to carefully test these secondary hypotheses.

